### Procedures

Participants will be recruited through postings on campus and nearby workplaces, pamphlets to Penn Medicine practices, internet advertisements, and local media appearances. Participants will complete an initial phone screen to determine eligibility and assess availability. Participant responses will be reviewed by the principle investigator and if they appear to be eligible, a screening visit will be scheduled. Study staff will complete a clinical interview assessing typical eating and sleep patterns, weight history, and psychiatric status. Participants will also be asked to complete several self-report questionnaires to assess mood, exercise, sleeping and eating patterns, and to examine psychological constructs related to eating and food. Participants will undergo a medical history and physical, and their weight, height, and waist circumference will be measured. Blood pressure, pulse, fasting blood work (which includes tests for a metabolic panel, fasting glucose, HbA1c, lipid panel, and CBC test), and an EKG will also be performed to exclude diabetes, MetS, and other metabolic or cardiac issues. Participants will receive logs to record food, physical activity, and sleep-wake cycles, as used in our previous studies of NES (135,136) and our R21 study, and an actigraph to wear for 10d. Upon completion, study staff will review their logs and actigraphs, and if they meet inclusion criteria, they will be scheduled to undergo the inpatient baseline assessment. After baseline assessment, participants will be randomized to begin the study with either the daytime or delayed eating condition, and they will receive their first 3d of food. The participants will also receive food, sleep, and exercise logs and actigraphs, which they will use for the study duration. Assessment Overview. Assessments will be conducted at 4 phases: 1) pre-eating condition 1; 2) post-eating condition 1; 3) pre-eating condition 2; and 4) post-eating condition 2 (Table 2). Each assessment will include 28h at the Center for Human Phenomic Science (CHPS) where participants will eat according to a standardized schedule. Participants will observe an overnight fast and arrive at CHPS at 0700h. Weight, height, waist circumference, and blood pressure will be measured. Participants will be asked to complete a series of questionnaires to assess psychological measures related to eating and food. Blood will be drawn at 4h intervals for 24h (0800h, 1200h, 1600h, 2000h, 2400h, 0400h and 0800h) to measure circadian rhythms of leptin, ghrelin, melatonin, cortisol and glucose, and of gene expression (43,90,92,95,98,137). A one-time blood sample will also be drawn for genomic analysis. Fasting levels of glucose, insulin, adiponectin, cholesterol, triglycerides, non-esterified fatty acids (NEFAs) and CRP will be measured at 0800h. At the same 4h intervals (0800h, 1200h, 1600h, 2000h, 2400h, 0400h and 0800h), a saliva sample will be obtained using salivette salivary swabs to collect information on changes to the salivary microbiome. This involves participants placing a cotton swab called a Salivette in their mouth to absorb saliva and placing it back into a small tube to be stored; they will be asked to refrain from using toothpaste, mouthwash, or gum beginning at 11 pm the night before admission for this test. After the initial fasting blood draw at 0800h, indirect calorimetry will assess REE and fuel oxidation (RQ) at 0900h. A standardized breakfast will then be served. Next, body composition will be measured using Dual Energy X-ray Absorptiometer (DEXA). At 1200h, blood will be drawn followed by lunch and harvesting of AT at 1300h. Following the AT procedure, participants will complete three computer-based cognitive tests administered by research staff. An afternoon snack, dinner, and evening snack will be served; the last snack will be consumed by 2100h. Participants will then fast overnight in preparation for the FSIGT, and blood draws will continue every 4h. At 0800h, the FSIGT will occur, followed by breakfast, and then discharge from the CHPS. [name], will be contacted in case of medical emergency. In his absence, we will call the hospital operator at [contact] and ask to speak to the endocrinology fellow on call. Dietary Plan and Food Distribution. Research staff will deliver meals and snacks from the CHPS metabolic kitchen 2x/wk, pick up uneaten food, and collect and provide new actigraphs. Participants may also choose to pick up food themselves from the metabolic kitchen if they prefer. Menus will accompany the meals, and participants will check off each food item they consume and note any modifications to their meals and snacks. The CHPS staff will provide portion size training at baseline. Participants will purchase their own beverages and record them on their menus. Mean beverage intake, as reported at baseline, will be factored into each participants total

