**Analysis Plan**

**Overview** Our study proposes a within-subjects cross-over design. With a pre- and post- measurement for both eating conditions per participant for the outcomes, this design allows for comparisons within subject over time and between conditions. We will design our subject randomization on a two-treatment Latin Square design randomized for available subjects. This will allow us to include effects from the order of treatment (delayed eating first vs. daytime eating first) in the mixed effects model as a treatment order effect. **General Approach** The first phase of the analysis will be descriptive. The sample will be characterized by demographic variables (e.g., age, gender, race and ethnicity), health status (e.g., BMI and medical status) and behaviors (e.g., physical activity, dietary habits, sleep and eating timing). Categorical variables will be summarized by frequencies, while continuous variables will be summarized by the mean and 95% confidence intervals, median, standard deviation and range. The predictor of interest for each aim will be the eating condition (daytime vs. delayed). An analysis of data distributional properties will be performed to determine if variance stabilizing or normalizing transformations should be applied to the outcome measures as a function of eating condition. The second phase of the analysis will consist of model building and interpretation. For within-group outcomes, all available data will be used to estimate changes over time. Other fixed covariates in the models will account for chance imbalances (not balanced by randomization, such as subject) at the start of the study. Group-by-time interaction terms will estimate the differences in changes over time between the daytime and delayed eating condition on each continuous outcome of interest. Further analyses will adjust for departures from randomization related to dropout or suboptimal adherence (e.g., eating or sleeping outside the assigned time window, eating non-provided meals, exercising more than allowed). Thus, separate models will be generated for each of the outcome measures, with each outcome measure regressed on eating condition assignment, along with baseline outcomes and any other covariates deemed prognostic in preliminary analyses, including adherence measures such as sleep and eating timing, and exercise. Since there are two orders (daytime-delayed or delayed-daytime), clustering of participants will be modeled using a fixed covariate to indicate order. Assessments from individuals repeated over time are more alike than expected by chance and failure to consider the non-independence of assessments will yield misleading results due to the underestimation of variance. Mixed effects models with random intercepts and slopes for participants will account for the within-subjects correlation. Thus, we expect the linear mixed models to account for fixed treatment and order effects, and random subject effects. Missing data are sometimes handled by removing individuals with incomplete data from the analyses, a strategy that may potentially produce biased estimates such that those with complete data do not represent the original sample. The proposed analytic method (mixed effects models) assumes that data are missing at random (i.e., missing data are dependent only on observed, past values of covariates and outcomes), and these models use all available data. This approach will not account for informative dropout, where dropout occurs for reasons related to unobserved outcomes. Thus, sensitivity analyses will be run to estimate the potential impact of missing data on overall response to the daytime and delayed eating phases assuming that those with no measurements fared worse than those who remained in the study (151). Bias from non-compliance may also occur if participants do not adhere to the prescribed eating conditions. Non-compliance may be associated with outcomes and act as a confounder. To address this potential issue and estimate the effect of the eating conditions in the presence of full compliance, we will implement instrumental variable methods (152,153). All analyses for these 3 aims will be performed in the latest versions of the analytical software programs, SAS (v 9.3), Stata (v 13) and R (v 3.3.3). **Approach by Specific Aim** **Specific Aim 1.** The goal of this aim is to compare the daytime vs. delayed eating schedule on body mass (weight), adiposity, and energy homeostasis outcomes. We will fit separate linear mixed effect models for each outcome as described above. Baseline covariates that are found to be associated with missing data or unbalanced after randomization will be added to the models. Appropriate contrasts will be estimated with 95% CIs to quantify the difference between the daytime vs. delayed schedules in the reduction of outcomes. **Specific Aim 2.** The goal of this aim is to compare the daytime vs. delayed eating schedule on the phase changes in the circadian ghrelin and leptin rhythms and the phase and cycling of gene expression profiles from blood. Analysis of the circadian phase of hormonal and

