
amplitude and phase of expression data will use linear mixed effects cosinor analysis (154), which accounts for systematic inter-individual differences. We will fit separate linear mixed effect models for ghrelin and leptin phases as described above. For transcriptomics, gene expression count data will be normalized in R using the TMM function in edgeR (155) and voom in the limma package (156). We will use linear mixed effect models against RNA-seq depth count data to test the differences in genes between the daytime and delayed conditions. Mixed model analysis will be done on the normalized RNA count data to adjust for effects such as condition order and random subject effects using the lme4 package (157) in the R statistical environment version R-3.2.3. P-values for each test will be generated from the lmer results using the Anova function in the R car package (158). Coefficients of the lme analyses will represent the log2 fold change between the two conditions tested (change in daytime vs. change in delayed). We will use a p-value cutoff adjusted by false discovery rate of 0.05 to detect all RNA changes of statistical significance comprehensively. Pathway analysis will be run in various functional enrichment analysis tools, e.g., Metacore (Thomson Reuters) and Ingenuity Pathway Analysis software (Qiagen). We also will cluster genes by phase for each of the 4h sample bins and compare them with circadian rhythm hormone phase profiles using correlational analysis to identify how different blood markers are related as a function of eating condition; this may allow for identification of additional genes implicated in timed eating. Each phase cluster can also be analyzed for statistical significance of enrichment against a number of biological pathways and gene sets. Specific Aim 3. The goal of this aim is to compare the daytime vs. delayed eating schedule on insulin sensitivity and free fatty acid dynamics and on AT gene expression. Changes in insulin sensitivity and free fatty acid dynamics by condition will be compared with linear mixed-effects models. Statistical analysis of gene expression data will be conducted as described for Specific Aim 2. As AT and blood will be collected on the same day, we will also compare pre-post changes in AT and blood expression using meta-analyses, to identify how different tissues relate to each other as a function of eating condition. This will also allow indirect comparison of hormonal data with AT gene expression. Finally, we will correlate AT gene expression with fasting lipid and glucose levels.

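### No period effect is pre-specified for the cross-over and time is left uncoded; under a pre/post coding this costs power and, with unequal completers per order, adds a small bias

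*Combined protocol and SAP*

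**What the plan says.** The design is a two-order cross-over: 8 weeks on each eating condition, separated by a 2-week washout (Study duration). Procedures lists the visits: "Assessments will be conducted at 4 phases: 1) pre-eating condition 1; 2) post-eating condition 1", followed by the same pair for condition 2. The Analysis Plan overview describes the data as "With a pre- and post- measurement for both eating conditions per participant for the outcomes".

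The General Approach defines the effect of interest: "Group-by-time interaction terms will estimate the differences in changes over time between the daytime and delayed eating condition". It does not say whether time has two levels (pre, post) or four (assessments 1 to 4). The order effect is described as "effects from the order of treatment (delayed eating first vs. daytime eating first", and the model summary is "Thus, we expect the linear mixed models to account for fixed treatment and order effects, and random subject effects". Random intercepts and slopes are planned for participants, and on missing data the plan says that "these models use all available data". Specific Aim 2 repeats condition order and subject as adjustments for gene expression, and says that "amplitude and phase of expression data will use linear mixed effects cosinor analysis". A period term (first versus second 8 weeks) is not named anywhere.

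On allocation the plan says only: "We will design our subject randomization on a two-treatment Latin Square design randomized for available subjects". Power (Accrual) rests on a two-sided paired t-test at alpha 0.05 with 36 of 40 participants retained.

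**The concern.** In a cross-over, the usual nuisance effect is that participants respond differently in the first and second periods, for example through season, fatigue with the regimen or declining adherence. Order is a between-participant factor and cannot remove a within-participant difference of this kind. The baseline value and random slopes do not remove it either.

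The pre/post description of the data makes pre/post the natural coding of time. On that coding, every Aim 1 primary outcome is analysed without adjustment for a period difference in change, and Aims 2 and 3 inherit the same model. Power is lost even if the orders finish perfectly balanced. If they do not, the treatment contrast is also shifted.

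The pilot-study reassurance in Procedures, that measures had returned to pre-condition levels, compares starting levels by condition. It says nothing about whether change differs by period.

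**Working it through.** **The plan's own figure.** 40 × 0.90 = 36, so the evaluable n reproduces. A two-sided paired t-test at alpha 0.05 with n=36 has 80% power at d = 0.48 (noncentral t, 35 df). The powers for individual variables cannot be reproduced because Table 1 is not in the available text. I use d = 0.48 as a reference effect.

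**Set-up.** Let D be the daytime change minus the delayed change for one participant, with SD sigma_D within order. Let tau be the treatment effect and delta the second-period change minus the first-period change. Then E[D] = tau − delta in the daytime-first order and tau + delta in the delayed-first order. The unadjusted estimate is the mean of D, and the period-adjusted estimate is the average of the two order means. With n1 and n2 completers:

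- size of bias without period = delta × |n1 − n2| / (n1 + n2)
- bias with period = 0

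**Splits.** Assume 20/20 allocation and 4 random dropouts (hypergeometric, C(40,4) = 91,390):

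- 18/18: 190² / 91,390 = 39.5%
- 19/17 either way: 2 × 20 × 1,140 / 91,390 = 49.9%
- 20/16 either way: 2 × 4,845 / 91,390 = 10.6%

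**Complete pairs, no period term.** Simulated power at tau = 0.48 sigma_D, for delta = 0.25 / 0.5 / 1.0 sigma_D:

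| Completers | Bias | Bias as % of d | Power, bias opposing | Power, bias favouring |
|---|---|---|---|---|
| 18/18 | 0 | 0 | 78 / 73 / 50% | same |
| 19/17 | 2/36 = 0.056 delta | 3 / 6 / 12 | 76 / 67 / 38% | 80 / 78 / 63% |
| 20/16 | 4/36 = 0.11 delta | 6 / 12 / 23 | 73 / 61 / 27% | 82 / 82 / 74% |

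With period in the model, power is 79–80% in every cell. Type I error without period is 0.6–4.6% across these cells, so the test is conservative. That does not extend to larger imbalance: at 22/14 it reaches 6.6% (delta = 0.5) and 7.5% (delta = 1.0).

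**All available data.** The planned mixed model would keep first-period data from dropouts. I took the exact generalised least squares expectation of the condition-by-post coefficient. Residual variance was 0.25 (so Var(D) = 4 × 0.25 = 1), random-intercept variance 4, and random pre/post slope variance 0 to 0.5, all in units of sigma_D². Dropouts were split 1 and 3 between the orders at 19/17, and 0 and 4 at 20/16.

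| Fixed effects added to condition × pre/post | Bias at 19/17 | Bias at 20/16 |
|---|---|---|
| order (as planned) | 0.028–0.042 delta | 0.056–0.084 delta |
| order + period + period-by-pre/post | 0.00 | 0.00 |
| order, with time as four visits | 0.00 | 0.00 |

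At slope variance 2.0 the planned model gives 0.05 and 0.10 delta. Adding order-by-time, or period as a main effect only, does not remove the bias.

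**Cosinor.** With seven samples per visit, a 24 h cycle and complete pairs, a 1 h period difference in phase change moves the phase contrast by 0.056 h at 19/17 and 0.11 h at 20/16. Period and period-by-pre/post without cosine and sine interactions leave this unchanged. With those interactions it is 0.00.

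**The case against.** The case against rests on five points.

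- **No harm is demonstrated.** No value of delta is given. The pilot used the same two-order design, so its effect sizes may already contain period variance. This stands: no shortfall against the stated power is shown.
- **The larger losses need a large delta.** D differs between orders by 2 × delta, so delta = 1.0 is a gap of two SDs. At delta = 0.25, power is 78% at 18/18 and 76% or 80% at 19/17, and these splits cover 39.5 + 49.9 = 89.4% of outcomes under the assumed allocation. This also stands; delta = 1.0 is only an upper bound.
- **The power figures at unequal splits are for complete pairs.** The plan uses all available data, which reduces the bias as shown. Power was not recomputed for that model, so the losses with an opposing bias are probably overstated.
- **Time may mean the four visits, and the covariate wording is open-ended.** Both readings are possible. But one adjusts for period and the other does not, and the plan does not choose. Leaving room for prognostic covariates is not pre-specifying one.
- **The cosinor bias is small.** It is 0.056 to 0.11 h, or 3 to 7 minutes, per assumed hour, with sampling every 4 h. The Aim 2 hormone phases already go into separate mixed models, so part of the remedy is close to what is planned.

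These points limit the size of the problem. They do not supply the missing term.

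**Conclusion.** The concern holds. The absence of a period term and of a coding for time is certain from the text, as is the direction of the effect under pre/post coding. The size is conditional on delta and on the split of completers, neither of which the documents give.

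For delta of 0.25 to 0.5 sigma_D and balanced completers there is no bias, and about 2 to 7 percentage points of power are lost from 80%. At 19/17 or 20/16 the complete-pair bias for the same delta is 3–12% of the reference effect, and it is smaller when all available data are used. Type I error stays at or below 5% under 20/20 allocation with 4 dropouts, but not at 22/14. If time is coded as four visits, the bias is zero. This is a pre-specification gap worth closing because the remedy is cheap, not evidence that the trial is underpowered.

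**What to change.** 1. State whether time is pre/post or the four assessments, and whether randomisation is balanced by order (and how).
2. Pre-specify period (first/second) as a fixed effect in every change-score or baseline-adjusted model.
3. In every four-assessment mixed model, including gene expression, pre-specify period and period-by-pre/post. Period as a main effect alone is not enough.
4. In cosinor models, let period and period-by-pre/post also interact with the cosine and sine terms. Alternatively, fit the period-adjusted change model to the per-visit phase and amplitude estimates.
5. Keep order as a secondary term.

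**Cost.** A few lines of text, and period is already recorded. The change uses one or two degrees of freedom in change and pre/post models, and six fixed parameters in a cosinor model (two terms, each on the intercept, cosine and sine). If there is no period effect, power without versus with the term is 80.0% vs 79.9% at 18/18, 80.0% vs 79.8% at 19/17 and 80.0% vs 79.4% at 20/16.

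### If the seven blood samples of a visit are pooled in one gene model with participant-level random effects only, the daytime-versus-delayed level test can be too liberal; a visit-level random intercept or one summary per visit would prevent this

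*Combined protocol and SAP*

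**What the plan says.** The Procedures section sets four inpatient assessments per participant, before and after each eating condition. Whole blood for transcriptomics is taken every 4 hours from 0800h to 0800h at each of them, which is seven samples per visit and 28 per participant.

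In the Analysis Plan, Specific Aim 2, linear mixed models are used "to test the differences in genes between the daytime and delayed conditions". The tested quantity is a difference of changes: "Coefficients of the lme analyses will represent the log2 fold change between the two conditions tested (change in daytime vs. change in delayed"). The gene model is to "adjust for effects such as condition order and random subject effects using the lme4 package", and a cutoff at a false discovery rate (FDR) of 0.05 is applied to the resulting p-values.

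The General Approach adds: "Mixed effects models with random intercepts and slopes for participants will account for the within-subjects correlation". It does not name the slope variable. It also describes two model forms. In one, "Group-by-time interaction terms will estimate the differences in changes over time between the daytime and delayed eating condition". The other is a model "with each outcome measure regressed on eating condition assignment, along with baseline outcomes". No visit-level random term is named in either place, and no clock-time term is named for the level test.

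**The concern.** The coefficient of interest varies only between a participant's four visits. The seven samples of one 24-hour stay may share something specific to that stay, such as recent diet, illness or sample handling. If so, they do not carry seven independent pieces of information about the contrast. A model with a participant intercept alone puts that shared variation into the sample-level residual and divides it by too large a count, so the standard error is too small.

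The General Approach states the principle itself: "failure to consider the non-independence of assessments will yield misleading results due to the underestimation of variance". As written, the plan applies it to participants but not to visits within participants. If the gene-wise p-values are too small, the 5% FDR is not assured for the blood genes declared, and the planned pathway analysis starts from that list.

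**Working it through.** **Inputs from the documents.** Analysed n = 40 × 0.90 = 36 (Accrual); 4 visits; 7 samples per visit. Observations: 36 × 4 × 7 = 1,008.

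**Assumed inputs.** The documents do not give r, the visit's share of within-participant variance, so a range is shown. Within-participant variance apart from clock time is set to 1. c is the common clock-time variance on the same scale.

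**True error of the contrast.** The visit mean square is V = 7r + (1 − r) = 1 + 6r, on 35 × 3 = 105 df.

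**Error used with a participant intercept and clock-time terms.** Residual df = 1,008 − 36 − 3 − 6 = 963, of which 963 − 105 = 858 are within visits. Residual = [105V + 858(1 − r)] / 963. Type I error = 2 × [1 − Φ(1.96 / √(V / residual))].

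| r | V | Residual | Ratio | Type I at 5% | Type I at 0.1% |
|---|---|---|---|---|---|
| 0 | 1.00 | 1.000 | 1.00 | 5.0% | 0.1% |
| 0.05 | 1.30 | 0.988 | 1.32 | 8.7% | 0.4% |
| 0.10 | 1.60 | 0.976 | 1.64 | 12.6% | 1.0% |
| 0.20 | 2.20 | 0.953 | 2.31 | 19.7% | 3.0% |

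The nominal 5% is reproduced at r = 0 only. Simulation of 20,000 null genes per share gave 5.0%, 9.0%, 12.5% and 20.0%.

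**Same model without clock-time terms.** Residual = [105V + 864(1 − r) + 1,008c] / 969. With c = 0 the results are again 8.7%, 12.6% and 19.7% for r = 0.05, 0.10 and 0.20. At r = 0.10:

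| c | Residual | Type I at 5% |
|---|---|---|
| 0.25 | 1.236 | 8.5% |
| 0.5 | 1.496 | 5.8% |
| 0.6 | 1.600 | 5.0% |
| 1.0 | 2.016 | 2.8% |

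The residual equals V when c = 6r, so the inflation is gone from that point on. At r = 0.05 and c = 0.25 the result is 5.5%.

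**Participant slopes (r = 0.10, clock-time terms included).**
- Four-visit model, slope on time: about 13%. Slopes on time and condition: about 14%. Neither helps.
- Four-visit model, slope on condition-by-pre/post: about 5.8%.
- Baseline-adjusted post-visit model, slope on condition: 70 of 1,200 null fits rejected, or 5.8%.

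Referring 1.96 to a t distribution gives 5.8% on both 34 and 35 df. The last two figures are therefore the normal-versus-t difference with 36 participants, with no visit inflation left.

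**With the error at visit level.** For r from 0 to 0.20, the same simulations gave 4.6% to 5.4% with a visit intercept and clock-time terms, and 4.9% to 5.1% for a t test on visit means.

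**Consequence for the FDR.** In simulations of 10,000 genes (participant intercept, clock-time terms, 10% of genes truly changing, the same r for every gene), the realised FDR at nominal 5% was 0.13, 0.23 and 0.43 at r = 0.05, 0.10 and 0.20.

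**The case against.** The strongest reply is that the documents do not commit to the model that fails.

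- **Pooling is not stated.** A reader might take "these models use all available data" as a statement that all seven samples enter one model. It comes from the missing-data discussion, where the contrast is with dropping incomplete participants, and it does not settle how clock times are handled. With visit summaries, or a separate model for each clock time, the problem does not arise. This stands, and it makes the point conditional.
- **The named slopes may already be enough.** If the participant slope is on the tested condition-by-pre/post term, or on condition in the baseline-adjusted post-visit form, the contrast has the right error. A reader might see the 5.8% as leftover visit inflation, but it is not. This also stands: the plan contains terms that could cure the problem, but does not say where they go. The list of effects for the gene model is also open-ended.
- **Size and direction depend on the gene.** The 9%, 13% and 20% series assumes little common clock-time variation, or clock-time terms that the plan does not name for this test. For strongly cycling genes without such terms the test can be conservative. This stands, and both sets of figures are needed.
- **Aim 2 is stated in terms of phase and cycling.** Those tests use a mixed-effects cosinor analysis, and the figures here do not apply to them. But the log2 fold change is described separately and reads as a test of level.

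None of this shows that a plain subject-effects fit to pooled samples would be safe.

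**Conclusion.** The concern holds in conditional form. If the seven samples of a visit are pooled with a participant intercept, or with participant slopes on time or condition in the four-visit model, the blood-gene level test is too liberal whenever visits differ and common clock-time variation is small or modelled. Its size rests entirely on the assumed visit share; at a share of zero there is no inflation.

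A reader might infer that the plan's blood-gene p-values are wrong and its 5% FDR is broken. The documents do not support that, because neither pooling nor the slope variable is specified. The supportable statement is that 5% is not assured under one natural reading.

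Adipose tissue is unaffected (one sample per visit), as are hormone phases estimated once per visit. Cosinor amplitude and phase tests were not assessed. Blood transcriptomics is a secondary outcome, so the matter is minor.

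**What to change.** In Specific Aim 2, for any blood model of expression level that pools the samples of a visit, add a visit-within-participant random intercept, (1|subject/visit) in lme4 notation, or analyse one summary per participant per visit. The same text should state whether samples are pooled, which of the two model forms applies, and what variable any participant slope is on.

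Clock-time fixed effects are an optional efficiency gain. At r = 0.10 without them, the visit intercept alone gives 5.3%, 4.9%, 4.5% and 2.8% at c = 0.25, 0.5, 0.6 and 1.0. It therefore stops the inflation, but leaves the test conservative for strongly cycling genes.

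The cost is one more random term, a little more computing and somewhat fewer genes declared. At r = 0.10 and nominal 5%, with clock-time terms, an effect that the corrected model detects with 80% power is declared about 90% of the time by the uncorrected one. No new data are needed.

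### Gene-level p-values come from car's Anova on lmer fits with no F test or degrees-of-freedom method; under a Wald chi-square reference the 5% false discovery rate need not hold with 36 participants, most clearly in adipose tissue

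*Combined protocol and SAP*

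**What the plan says.** Under Specific Aim 2 of the Analysis Plan, counts are normalised with TMM and voom, and a mixed model is then fitted gene by gene with lme4: "Mixed model analysis will be done on the normalized RNA count data to adjust for effects such as condition order and random subject effects". The tested quantity is a contrast of changes: "Coefficients of the lme analyses will represent the log2 fold change between the two conditions tested (change in daytime vs. change in delayed").

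The inference step is "P-values for each test will be generated from the lmer results using the Anova function in the R car package". Selection follows: "We will use a p-value cutoff adjusted by false discovery rate of 0.05 to detect all RNA changes of statistical significance comprehensively". Specific Aim 3 applies the same method to adipose tissue.

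The general approach, earlier in the Analysis Plan, states: "Mixed effects models with random intercepts and slopes for participants will account for the within-subjects correlation". It does not say which term carries the slope, and the gene-level text mentions only random subject effects.

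The Accrual section expects 36 completers from 40 enrolled. Blood for RNA is drawn seven times at each of four visits; adipose tissue is taken once per visit. The plan does not state the test statistic, a df method, the FDR procedure, the number of genes or the share expected to change.

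**The concern.** A Wald chi-square test treats the estimated variance as if it were known. With a few dozen df its tail is too thin. The discrepancy is small at p = 0.05 but grows quickly further out. FDR selection across thousands of genes works at cut-offs of roughly 0.0005 to 0.005, so a check of the model at the 5% level would not reveal the problem.

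The gene lists feed the pathway analysis, and the Background section presents genes found in both tissues as candidate biomarkers and targets. A list labelled 5% FDR could contain two or three times that share of false genes if few genes truly respond to meal timing. If none respond, it could report findings far more often than the label implies.

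**Working it through.** **Inputs from the documents.** n = 36 (Accrual; 40 × 0.9 = 36 reproduces). Samples per participant: adipose 4 × 1 = 4, blood 4 × 7 = 28. FDR target 0.05.

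**Assumptions.** The default Wald chi-square is kept; for one contrast this equals a normal reference. The FDR procedure is Benjamini-Hochberg. There are 15,000 independent genes. Changed genes have standardised contrast d, so the noncentrality is d√36 = 6d.

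**Degrees of freedom under different readings of the random effects.**
- One contrast per participant, adjusted for order: 36 − 2 = 34.
- Four samples, random intercept plus one slope not on the tested contrast: 36 × 3 − 3 fixed terms − 35 = 70.
- Four samples, intercept only: 36 × 3 − 3 = 105.
- 28 blood samples, intercept only: 36 × 27 − 3 = 969, about 970.

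**Per-test error.** True p = 2·P(t_df > z), with z the normal quantile of the nominal p.

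| Nominal p | 34 df | 70 df | 105 df |
|---|---|---|---|
| 0.05 | 0.058 | 0.054 | 0.053 |
| 0.001 | 0.0023 | 0.0016 | 0.0014 |
| 0.0001 | 0.00044 | 0.00023 | 0.00018 |

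**Realised FDR.** Let π be the share of changed genes. For a nominal cut-off c, let F0(c) and F1(c) be the true rejection probabilities for unchanged and changed genes. With many genes, Benjamini-Hochberg solves c / G(c) = 0.05, where G = (1 − π)F0 + πF1. Realised FDR is (1 − π)F0 / G.

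Example (34 df, π = 1%, d = 0.8): c = 0.00052, F0 = 0.00143, F1 = 0.894. Then G = 0.99 × 0.00143 + 0.01 × 0.894 = 0.01036, and c / G = 0.05 as required. FDR = 0.001416 / 0.01036 = 13.7%. With the correct t reference F0(c) = c, so FDR = 0.05 × (1 − π) = 4.95%.

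Results for d = 0.8, normal reference:

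| Share changed | 34 df | 70 df | 105 df | 970 df | t reference |
|---|---|---|---|---|---|
| 1% | 13.7% | 8.6% | 7.2% | 5.2% | 4.95% |
| 5% | 8.9% | 6.6% | 6.0% | 4.9% | 4.75% |
| 10% | 7.3% | 5.8% | 5.4% | 4.6% | 4.5% |
| 30% | 4.7% | 4.1% | 3.9% | 3.5% | 3.5% |

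With d = 0.5 and 1% changed, the figures are 19.3% at 34 df, 10.8% at 70 df and about 8.5% at 105 df.

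**No gene changed.** The smallest Benjamini-Hochberg threshold is 0.05 / 15,000 = 3.3 × 10⁻⁶, or z = 4.65. At 34 df the true tail probability there is 4.87 × 10⁻⁵, and 1 − (1 − 4.87 × 10⁻⁵)^15,000 = 0.52. The same step gives 0.20 at 70 df, 0.14 at 105 df and 0.055 at 970 df. Simulating the full step-up procedure (2,000 replicates) gives about 57%, 22%, 16% and 6%, against about 5% with the t reference.

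**The case against.** Four counter-arguments deserve weight.

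*The plan never says Wald chi-square.* This is correct. The default is software behaviour, and the same function can return an F test for lmer fits. A reader might infer that the plan prescribes an invalid test; the text does not support that. It does, however, name a specific route to the p-values and no option that would make them small-sample p-values, so it needs the same one-line change either way.

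*No single inflated FDR belongs to this plan.* This stands. A reader might take a figure such as 7 to 13% as a property of the design. That range needs a small share of changed genes, and the documents give no share, effect size or gene count. Realised FDR runs from about 5% or less at 30% changed to about 19% at 1% changed with d = 0.5 and 34 df.

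*Blood may be unaffected.* This stands for a random-intercept model, where about 970 df make the chi-square nearly exact. But that model leaves out the slopes of the general approach. If they sit on the tested contrast, the information is again at participant level, near 34 df. For adipose tissue no reading gives more than about 105 df.

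*The precision weights from voom may be used after all.* A reader might infer that they are discarded, because the plan names "voom in the limma package" under normalisation and later says "Mixed model analysis will be done on the normalized RNA count data". The plan is silent on weights, and silence does not show that they are dropped. This is not part of the point.

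**Conclusion.** The point holds conditionally. If the default Wald chi-square is kept, the gene-level p-values are too small in the tail where the FDR cut-off works. For adipose tissue, at 34 df and d = 0.8, realised FDR is about 14%, 9%, 7% and 5% with 1%, 5%, 10% and 30% of genes changed. At 70 to 105 df it is about 5 to 11% for 1 to 10% changed, across d = 0.5 to 1.0. If nothing changes, the chance of at least one false discovery is about 15 to 60% over 34 to 105 df, against about 5%. Blood shares the problem only if the participant slope is on the tested contrast.

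These figures rest on the assumed statistic, Benjamini-Hochberg, independent genes, and assumed gene count, share changed and effect size. Transcriptomics is a secondary outcome; weight, DEXA and calorimetry are untouched. The plan should still be changed, because the correction is available at little cost and the 5% label cannot otherwise be relied on.

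**What to change.** In the Specific Aim 2 text, replace the sentence on p-values with one stating that each gene's contrast is tested by an F test with Kenward-Roger (or Satterthwaite) df from the lmer fit, and that the FDR adjustment is applied to those p-values. Name the FDR procedure in the same sentence.

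State the random-effects structure for each tissue. In blood, with 28 samples per participant, put the participant-level slope on the tested contrast. In adipose tissue each participant supplies only one value of that contrast, so such a slope cannot be separated from residual error; there the df method carries the correction. Aim 3 inherits the wording through its cross-reference.

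The cost is an option in the code, extra computing time over thousands of fits, and shorter gene lists. In the example at 34 df, 1% changed and d = 0.8, the list falls from about 155 genes (15,000 × 0.01036), 21 of them false, to about 126, 6 of them false (with the t reference, c = 0.00042 and F1 = 0.797: 15,000 × [0.99 × 0.00042 + 0.01 × 0.797]). About 14 or 15 true genes are lost as well. With 10% changed the list shortens by about 5%, from 1,574 (15,000 × [0.9 × 0.00855 + 0.1 × 0.9726]) to 1,502 (15,000 × [0.9 × 0.00501 + 0.1 × 0.9564]). No new data are needed.
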